6.2 Prior and Concomitant Therapy

Patients are allowed to continue their usual treatment for Alzheimer's disease during the trial; it should remain stable throughout the study duration.

For subjects receiving at least one dose of the IMP, all relevant treatments (at the Investigator's opinion) administered during the 6 months prior to the screening visit for any indication and for Alzheimer's disease will be recorded in the eCRF, including the trade and generic names of the medication, the dose, the route of administration, and the duration of the medication (frequency). For subjects who do not receive at least one dose of the IMP (e.g. screening failure subjects), only the concomitant medication used to resolve SAEs reported during the screening period, will be collected in the eCRF.

6.2.1 Prohibited Medications Prior to Study Participation

As described in the Exclusion Criteria:

- Treatment within 30 days prior to visit 0 with systemic corticosteroids or other immunosuppressant's.
- Vaccination against influenza or any other vaccination, within 2 months before first IMP dose.
- Participation in another clinical trial within the previous 1 month to screening visit, or within the previous 12 months after the last dose to the screening visit in the case of subjects who participated in trials with a study drug whose intention was to modify the progression AD. The patient cannot be included in the study if the experimental drug was an immunotherapeutic drug, including IVIG or a vaccine against Alzheimer's disease.
- Patients with alcohol or drug abuse or dependence.

6.2.2 Prohibited Concomitant Medications during the Study

Administration of any of the following drugs interferes with the assessment and interpretation of clinical trial results and, therefore, any patient taking these drugs is not eligible for participation in the trial. These drugs are also prohibited during the whole study follow-up:

- Treatment with immunosuppressive drugs
- Treatment with experimental immunotherapeutics including IVIG or vaccines for Alzheimer's disease

6.2.3 Restricted Concomitant Medications during the Study

This section describes medications that are restricted but not prohibited during the study participation:

- Sedatives will not be permitted the night before the neuropsychological tests, particularly neuroleptics.
- Avoid administration of the influenza vaccine or any other vaccination during the 1 month prior and 15 days after each vaccination or until next Safety visit, whatever occurs earlier.
- If a patient with MCI needs to start a dementia treatment or a patient with AD needs modification of their dementia treatment before Int-6m visit (or V16B) or between Int-6m and V21visits (or between V16B and V21B), the investigator should discuss with him/her the benefit/risk balance in order to evaluate if the change can wait until after the Int-6m (or V16B) or V21 visit (or V21B), respectively. If the modification needs to be done before Int-6m (or V16B) visit or between Int-6m and V21 visit (or between V16B and V22B), respectively, the subject must be discontinued from the study treatment, but not from the study follow-up (see Section 5.3.4).
- Treatment with benzodiazepines and nootropics is authorized only at regular and stable doses in steady state (chronic use). Any dose change or treatment modification during the study will be reported both as an Adverse Event and as a change in the Concomitant medication section of the eCRF. If a patient needs to modify the dose before Int-6m (or V16B) visit or between Int-6m and V21 visits (or between V16B and V22B), the decision for the patient to continue with the study treatment will depend on clinical judgment and will be assessed on a case-by-case basis by the Medical Advisor.

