8.3.3 Adverse Event Definitions

8.3.3.1 Adverse Events

An AE is defined as any untoward medical occurrence in a subject or clinical investigation subject administered a medicinal product or study treatment and which does not necessarily have a causal relationship with this administration. An AE can therefore be any unfavorable and unintended sign (including any abnormal laboratory finding, for example), symptom, or disease temporally associated with the use of a medicinal product, whether or not considered related to the medicinal product.

The frequency of adverse events should be investigated using indirect questions at each study visit (e.g., How are you today? How do you feel?). Adverse events can also be detected when the patient directly and spontaneously reports them during a visit or between visits or by physical examination, blood test and other assessments. Abnormal laboratory parameters are only considered as an adverse event if the researcher classifies them as "clinically significant".

Alzheimer's Disease clinical signs or symptoms and pathological laboratory parameters are not considered adverse events if already present in the first assessment, except when deterioration or increase in frequency is observed.

All adverse events will be documented in a specific form for adverse events. The documentation includes the following information:

- Duration (start and end date),
- Intensity (mild, moderate, severe),
- Possible causal relationship with study treatment (related or not),
- Action taken (no measure taken, adjust dose/temporarily stop study drug, permanently discontinue study drug, administer concomitant medication, provided a nonpharmacological therapy, brief or prolonged hospitalization)
- Assessment of outcome (full recovery, improvement, unchanged, deterioration),
- Meet any of the severity criteria.

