9.1.3.1 Primary Safety Analysis

The primary safety variable is the frequency (%) of Adverse Events (AEs). The primary safety endpoint will be analyzed descriptively in the Safety population. For this primary safety analysis, the amyloid-PET negative and the amyloid-PET positive subjects within each treatment group will be pooled together.

The trial will be considered satisfactory if the pattern of AEs (overall or grouped as neurological, psychiatric or cardiovascular) is consistent with a good safety and tolerability profile of ABvac40 for human administration.

All AEs will be coded using the last version of the MedDRA dictionary where neurological AEs corresponds with the System Organ Class (SOC) Nervous system disorders, psychiatric AEs corresponds with the SOC Psychiatric disorders, and cardiovascular SOC corresponds with Vascular Disorders and Cardiac disorders.

The number and percentage of patients in each treatment group reporting at least 1 occurrence of an AE for each unique SOC and PT will be tabulated. AEs will be also tabulated by severity and by the relationship to study medication in each treatment group as assessed by the investigator. Patients who experienced multiple adverse events with the same PT will be counted once for the summaries, using the worst severity. Specific tables will be provided for AEs of special interest such as neurological, psychiatric and cardiovascular AEs.

As an exploratory analysis, the incidence of AEs (overall or grouped as neurological, psychiatric or cardiovascular) will be compared between the group receiving the active treatment (ABvac40) and the control group receiving placebo. Fisher's exact test will be used for these analyses.

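### Protocol 6.2.3 makes every benzodiazepine or nootropic change an adverse event whatever its cause, so changes with no untoward event enter the AE rate; the effect on the overall rate is small

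*Protocol*

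**What the plan says.** Protocol 6.2.3 allows benzodiazepines and nootropics only in stable chronic use, and then adds: "Any dose change or treatment modification during the study will be reported both as an Adverse Event". The same change is entered a second time with the patient's other medication data. Nothing limits this to changes prompted by a symptom or diagnosis.

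Protocol 8.3.3.1 defines the event differently: "An AE is defined as any untoward medical occurrence in a subject or clinical investigation subject administered a medicinal product or study treatment". It continues: "An AE can therefore be any unfavorable and unintended sign", and extends this to symptoms and diseases. In the same section, medication appears among the possible actions taken for an AE: "administer concomitant medication, provided a nonpharmacological therapy". Protocol 8.3.8 prefers a diagnosis as the AE term and has a separate field for other action to treat the event.

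The primary safety variable is the rate (%) of AEs (Protocol 8.1 and 9.1.3.1). Protocol 9.1.3.1 counts patients with at least one AE by SOC and PT, and adds: "Specific tables will be provided for AEs of special interest such as neurological, psychiatric and cardiovascular AEs". SAP 7.2.1 classes as treatment-emergent any AE that starts or worsens during or after the first administration, and reports counts and percentages of patients.

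**The concern.** Two sections of the protocol give sites different instructions. Under 8.3.3.1, a dose reduction because the patient is better is not an AE. Under 6.2.3 it must be entered as one.

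The 6.2.3 rule is also out of line with the rest of the protocol. Laboratory and vital-sign abnormalities become AEs only if the investigator judges them clinically significant (8.2.2, 8.2.3). Examination, EKG and MRI findings must be new or worse (8.2.4 to 8.2.6). The bullet in 6.2.3 on changes to dementia treatment has no AE rule at all. A bare dose change also has no natural place in the severity grades of 8.3.5, which describe how far an event disturbs normal activities.

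The trial's safety conclusion rests on the pattern of AEs, overall and by neurological, psychiatric and cardiovascular group. Records that are not untoward events add background to that pattern, and a reader of the tables could not tell them apart.

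**Working it through.** **1. Does the 6.2.3 rule reach the primary safety variable?** A change-only entry made after the first dose meets the treatment-emergent definition in SAP 7.2.1, because that definition looks only at onset or worsening. It is then counted by SOC and PT under Protocol 9.1.3.1 and SAP 7.2.1. The list of changes to protocol-specified analyses in SAP 9.2 does not mention these records. No section of either document flags or removes them.

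**2. The plan's own safety figure.** Protocol 9.2 and SAP 3.2 give 60 patients per arm for at least a 95% chance of detecting an AE with a true rate of 5%. The rule of three gives 3 / 0.05 = 60. Exactly, 1 − 0.95^60 = 0.954. The figure reproduces and does not depend on this point.

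**3. Effect on the overall any-AE incidence.** Let p be the incidence of patients with a genuine AE. Let q be the share of patients with a reportable change but no untoward event behind it. With q independent of p, the observed incidence is p + (1 − p)q.

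- p: Phase I values from Protocol 2.2, Table 1, used as illustration only: 68.75% (ABvac40, 11 of 16) and 87.5% (placebo, 7 of 8).
- q: not given in the documents. Assumed range 2%, 5%, 10%.

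| q | patients per 60 | observed at p = 68.75% | observed at p = 87.5% |
|---|---|---|---|
| 2% | 1.2 | 68.75 + 31.25 × 0.02 = 69.38% (+0.63) | 87.5 + 12.5 × 0.02 = 87.75% (+0.25) |
| 5% | 3 | 68.75 + 31.25 × 0.05 = 70.31% (+1.56) | 87.5 + 12.5 × 0.05 = 88.13% (+0.63) |
| 10% | 6 | 68.75 + 31.25 × 0.10 = 71.88% (+3.13) | 87.5 + 12.5 × 0.10 = 88.75% (+1.25) |

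The shift is about 0.3 to 3.1 points. It is small because a change-only record moves the overall percentage only for a patient with no other AE. If such changes fall mostly on patients who already have an AE, the shift is smaller still. In the opposite extreme, where none of these patients has another AE, the shift is q itself.

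**4. Effect in a low-rate category, if the records were coded there.** At p = 12.5% (Phase I psychiatric AEs in both arms), the same formula gives 12.5 + 87.5 × 0.02 = 14.25%, 12.5 + 87.5 × 0.05 = 16.88% and 12.5 + 87.5 × 0.10 = 21.25%. This is conditional. Protocol 9.1.3.1 defines the groups by MedDRA SOC, and neither document says which SOC a dose-change entry would receive.

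**The case against.** The best defence is that broad capture is deliberate. These drugs are allowed only at stable doses, so any departure is worth flagging, and 8.2.4 to 8.2.6 also record every new or worsened finding without a clinical-significance filter. The authors may also have meant that the reason for the change should be reported. In many cases there will be a real symptom, and that symptom is a valid AE.

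Part of this stands. Where a change has an untoward cause, an AE is due under either section. Double entry of cause and change adds little, because the planned tables count patients rather than records and 8.3.8 asks for a diagnosis and for related findings to be grouped. What remains is the change with no untoward cause. A new examination or MRI finding is at least a finding in the patient; a taper or a product switch need not be. If the intention was to capture the reason, the text does not say so, and sites must follow the text.

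A second objection concerns how such records are handled. Taking investigator-reported AEs out of the treatment-emergent tables would depart from the SAP's own counting rule and bring judgement into the primary safety outcome. That objection is sound, and the fix below leaves the main tables whole.

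**Conclusion.** The contradiction between Protocol 6.2.3 and 8.3.3.1 is real, and following 6.2.3 counts some non-events in the AE rate. The size is modest: about 0.3 to 3.1 points on overall any-AE incidence, assuming 2% to 10% of patients have change-only records, independence from other AEs, and Phase I incidences as the base. This is a minor point of wording and presentation.

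A reader might infer three stronger conclusions, which the documents do not support:

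- **That the safety comparison loses power.** The primary safety analysis is descriptive. Protocol 9.1.3.1 calls its Fisher comparison exploratory. SAP 7.2.1 plans only counts and percentages, across Parts A and B, and SAP 1.1 gives the SAP primacy over the protocol. Nor can every dose change be taken as a spurious AE, since some have a genuine AE as their cause.
- **That the psychiatric or neurological group is inflated.** The drug class makes this a natural guess, but the coding of such records is not stated, so only the conditional illustration above is possible.
- **That a dose-change term above 5% would defeat the sample size.** The 5% is an input to a detection probability in the ABvac40 cohort. It is not a threshold for a preferred term, and another term above it leaves the 0.954 unchanged.

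**What to change.** **Protocol.** Reconcile 6.2.3 with 8.3.3.1. Record a benzodiazepine or nootropic change in the concomitant medication section. Report as the AE the sign, symptom or diagnosis behind it, if there is one and it meets 8.3.3.1. This concerns recording only and leaves the rules on use of these drugs and on continuing study treatment as they are.

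**SAP 7.2.1, for data already entered.** Before database lock and while blinded, flag AE records that consist only of such a change. Keep them in the main treatment-emergent tables, list them, and show the overall and the neurological, psychiatric and cardiovascular incidence with and without them.

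**Cost.** One protocol sentence, one flag, one listing and one extra summary. Sites must state the reason for each change. The blinded review in SAP 3.1.3 and 3.4 is described for protocol deviations and per-protocol membership, so the flagging is a small added task there. No genuine event is lost, because the cause of a change remains reportable.

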6.3 Treatment Compliance

Treatment compliance is ensured because all treatments will take place at the trial center and will be administered by trained staff from each site.

Nevertheless, the reasons for any deviation from the administration of less than 100% of the investigational product dose as prepared must be recorded in the case report form (eCRF) and in the subject's medical records.

7 ASSESSMENT OF EFFICACY

7.1 Efficacy Variables

7.1.1 Part A

7.1.1.1 Primary Efficacy Variable

- Maximal increment of specific anti-A β 40 antibody signal (antibody titers estimated by ELISA [signal optical density (OD) values]) in each subject with regard to the pre-treatment visit (either V0 or V1)

7.1.1.2 Secondary Efficacy Variables

- Characterization of the immune response:
 - o Levels of anti-KLH and anti-A β 42 antibodies in plasma
 - o Level of anti-A β 40 antibodies in CSF
 - o Levels of cytokines in plasma including IL-2, IL-4, IL-5, IL-6, IL-10, IL-13, IL-15, TNF- α and IFN- γ (Sandwich ELISA)
 - o Analysis of the peripheral blood cell subsets by immunophenotyping
 - o Levels of antibody-secreting cells and cytokine-secreting cells (including IFN- γ , TNF- α and IL-13)
- Assessment of disease biomarkers:
 - o Levels of A β peptides in plasma
 - o Levels of cortical fibrillary amyloid deposition; as standardized uptake value ratio (SUVR) in amyloid-PET scans.
 - o Levels of CSF biomarkers (A β 42, Tau, P-tau, neurofilament light and neurogranin) and other A β peptide species
 - o Brain volumetric and atrophy of the hippocampus assessed by magnetic resonance imaging.
- Assessment of cognition, suicide risk and quality of life:
 - o Mini Mental State Examination (MMSE)
 - o Clinical Dementia Rating scale (CDR)
 - o Repeatable Battery for the Assessment of Neuropsychological Status (RBANS)
 - o Columbia Suicide Severity Rating Scale (C-SSRS).
 - o ADCS-ADL MCI
 - o Trail Making Test (TMT)
 - o Investigator Global Evaluation (IGE)
 - o Euroqol 5 Dimensions (EQ-5D)

7.1.2 Part B

7.1.2.1 Exploratory Efficacy Variables

- Maximal increment of specific anti-A β 40 antibody signal (antibody titers estimated by ELISA (signal OD values) in each patient with regard to the pre-treatment visit (either V0/V1 [Booster group] or V1B [Delayed start group]).
- Characterization of the immune response:
 - o Level of anti-A β 40 antibodies in CSF
 - o Levels of antibody secreting cells
- Assessment of disease biomarkers:
 - o Levels of A β peptides in plasma
 - o Cortical fibrillary amyloid deposition assessed by PET scans.
 - o Levels of CSF biomarkers (A β 42, Tau, P-tau, neurofilament light and neurogranin) and other A β peptide species
 - o Brain volumetric and atrophy of the hippocampus using magnetic resonance imaging
- Assessment of cognition and quality of life:
 - o MMSE
 - o CDR scale
 - o RBANS
 - o ADCS-ADL MCI
 - o C-SSRS
 - o TMT
 - o IGE
 - o EQ-5D-5L

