Additionally, after all patients complete their 18-months visit (V23), a statistical analysis will be performed to determine whether the Part B of the study should be discontinued.

Within the first week (3 ± 3 days) after each vaccination visit, a telephone control interview will take place.

Two weeks after each vaccination, and at 40, 50, 77 and 104 weeks there will be a safety visit consisting on:

- Physical and neurological examination (assessment of vital signs; electrocardiogram in five visits: V0, V16, V21, V23 and the final visit (V25); body biometrics; collection of adverse events and concomitant medication) at all face to face visits (V0, V1, V3, V4, V6, V7, V9, V10, V12, V13, V15, V16, V17, V18, V20, V21, V23 and V25; and PDV, if applicable).
- Blood collection for safety control and measurement of biological activity at visits: V0, V1, V3, V6, V9, V12, V15, V16, V17, V20, V21, V23 and V25
- A MRI at visits V0, V9, V16, V17, V21 and V25.

At the screening visit (V0), the participants will receive an amyloid-PET scan. Subjects will undergo additional amyloid-PET scan at V21 and final visit (V25) for the assessment of amyloid burden. The subject will receive lumbar puncture for CSF analysis at baseline (V1), V21 and at the final visit (V25) for the assessment of changes in CSF biomarkers.

Part B:

The Part B of the study will last for 18 months (from V1B to V22B). The scheme of visits will mirror the Part A scheme.

The first visit of Part B (V1B) will take place at least 18 months after the patient started Part A (i.e. he/she should have completed V23 of Part A to enter Part B).

The patients randomized to the placebo group during Part A will receive five monthly (every four weeks) immunizations with ABvac40 plus a booster shot after 6 months (Delayed start group), whereas the patients randomized to the Verum group during Part A will receive placebo following this schedule, except in V13B, where they will receive an ABvac40 booster shot

(Booster group). Given the extended inclusion period of Part A, the V13B booster will take place at different timepoints relative to the patients' last immunization. For the analysis, they will be grouped in 2 periods: 12 ± 3 months and 18 ± 3 months after their last Part A immunization.

Within the first week (3 ± 3 days) after each vaccination visit, a telephone control interview will take place.

Two weeks after each vaccination, and at 40 and 50 weeks there will be a safety visit consisting on:

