22. Participation in another clinical trial within the previous 1 month to screening visit, or within the previous 12 months after the last dose to the screening visit in the case of subjects who participated in trials with a study drug whose intention was to modify the progression AD unless documentation of receipt of placebo is available. The patient cannot be included in the study if the experimental drug was an immunotherapeutic drug, including IVIG or a vaccine against Alzheimer's disease unless documentation of receipt of placebo is available.
23. Patients with alcohol or drug abuse or dependence.
24. Absolute (having a pacemaker or implantable defibrillator) or relative (bare metal stent or stent implanted in the last six months) contraindications to MRI examination. Feeling of claustrophobic do not let perform MRI or PET scan.

25. Patients unlikely to comply with the protocol (e.g., unable to return for follow-up visits).
26. Women of childbearing potential, pregnant or nursing. Note: All women will be considered to be of childbearing potential unless they are postmenopausal (amenorrheic for at least 12 consecutive months, in the appropriate age group, and without other known or suspected cause) or have been sterilized surgically (i.e. bilateral tubal ligation, total hysterectomy, or bilateral oophorectomy, all with surgery at least 1 month before dosing)
27. Significant alterations in the EKG that are associated with an added risk for the patient.

Investigational Product, Dose and Mode of Administration

Study Medication

Name: ABvac40

Active ingredient: Conjugated A β x-40 to KLH

Transporter: Phosphate buffer containing 0.35% aluminium hydroxide (adjuvant)

Pharmaceutical Form: Injection ready vials

Posology: Part A: Verum group: Six administrations: the first five administered once every 4 weeks (28 \pm 3 days) and the sixth at week 42 (V18), 26 weeks after the fifth immunization. Each administration consists of 1mL injection of ABvac40 (containing 0.2 mg of Abetax-40).

Part B: Delayed start group: Six administrations: the first five administered once every 4 weeks (28 \pm 3 days) and the sixth at week 42 (V18B), 26 weeks after the fifth immunization.

Booster group: One administration at week 16 (V13B).

Each administration consists of 1mL injection of ABvac40 (containing 0.2 mg of Abetax-40).

Method of administration: Subcutaneous injection.

Duration of Treatment:

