3.2.2 Exploratory Efficacy Objectives

3.2.2.1 Immunogenicity

- To assess the immune response produced by repeated doses of ABvac40 after delayed start in patients receiving placebo during Part A.
- To assess the immune response triggered by a second ABvac40 booster in patients receiving ABvac40 during Part A.

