7.2.1.1 Assessment and characterization of the immune response

For the assessment and characterization of the immune response blood samples will be collected at visits V0, V1, V3, V6, V9, V12, V15, V16, V17, V20, V21, V23 and V25 (Part A), and at visits V1B, V3B, V6B, V9B, V12B, V15B, V16B, V17B, V20B, V21B and V22B (Part B). All these analysis, together with the levels of A β peptides in plasma, will be centralized at the Araclon-Grifols.

The laboratory tests to be performed with these samples are listed below. (Detailed descriptions of the laboratory test procedures are located in the study Laboratory Manual document):

- Characterization of the antibodies generated by vaccination with ABvac40: it will proceed to the titration of antibodies generated against the immunogenic peptide (A β x-40), other vaccine components (KLH) and A β -42 peptide. The specificity and isotype of these antibodies will also be characterized. These analyzes will be carried out in plasma samples by Enzyme-Linked ImmunoSorbent Assay (ELISA).

For the Part A, patients in the verum group will be classified as “Positive Responders” when their maximal increment ($M\Delta$) of anti-A β 40 specific antibody signal (OD in ELISA) from the pre-treatment visit (either V0 or V1) is equal or greater than 3 times the standard deviation of the titration ELISA. The antibody titers (defined as the inverse of the maximal plasma sample dilution which showed an OD increase ≥ 3 SD with regard to the preimmune sample) of Positive Responder patients will be reported.

- Analysis of cytokines in plasma: quantitation of a panel of cytokines in order to characterize the type of immune response (Th1 or Th2) by sandwich ELISA [Part A].
- Analysis of antibody-secreting cells: quantitation of B-lymphocytes secreting antibodies against A β or other components of the vaccine. This analysis will be performed by Enzyme-Linked ImmunoSpot (ELISpot) assay.
- Analysis of cytokine-secreting cells: quantitation of cells secreting cytokines in order to characterize the potency and type of immune response (Th1 or Th2). This analysis will be performed by ELISpot assay [Part A].
- Immunophenotyping of circulating blood cells: Quantitation of the relative number of peripheral blood mononuclear cells (cluster of differentiations; CD) to monitor the effect of the vaccine at cellular level. This analysis will be performed by multicolor flow cytometry [Part A].

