Analysis for antibody titration and determination of A β peptide and cytokine levels will be carried out at Int-6m (V16) and Final visit (V25/V23) [Part A] and at V22B (Part B), once the samples from all the subjects are available. Analysis of antibody-secreting cells [Part A and Part B], cytokine-secreting cells [Part A] and the immunophenotyping [Part A] will be performed subject by subject, immediately after each visit upon receiving the sample in the laboratory.

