4.2.2 Secondary Outcome Variables

4.2.2.1 Characterization of Immune Response

- Levels of anti-keyhole limpet hemocyanin (KLH) (Part A and Part B) and anti- $A\beta$ 42 antibodies in plasma (Part A only - anti- $A\beta$ 42 antibodies in plasma are not analysed by Araclon)
- Level of anti- $A\beta$ 40 antibodies in Cerebrospinal Fluid (CSF)
- Level of anti- $A\beta$ 40 antibodies in plasma

- Analysis of the peripheral blood cell subsets by immunophenotyping – Part A only (not analysed by Araclon)
- Levels of antibody secreting cells (only analysed in Part A and not analysed in Part B)
- Levels of cytokine-secreting cells (IFN- γ and IL-4) – Part A only (samples from only a small number of patients were analyzed. Hence, data for this analysis will not be reported)

4.2.2.2 Assessment of disease biomarkers:

- Levels of A β 40 and A β 42 peptides in plasma
- Cortical fibrillary amyloid deposition assessed by a-PET scans.
- Levels of CSF biomarkers [A β 42, A β 40 (Part A and B) and Tau, P-tau, neurofilament light and neurogranin (Tau, P-tau, neurofilament light and neurogranin were only analysed in Part A and were not analysed in Part B)] and other A β peptide species (other A β peptide species were not analysed by Araclon) (Part A and Part B)
- Brain volumetric changes (including hippocampal and ventricle changes) and atrophy of the hippocampus using MRI.

4.2.2.3 Assessment of cognition and quality of life:

- Mini Mental State Examination (MMSE):
 - an 11-question measure that tests five areas of cognitive function: orientation, registration, attention and calculation, recall, and language. The maximum score is 30. A score of 23 or lower is indicative of cognitive impairment
 - the following parameters will be summarized/analyzed as outlined in section 6.3:
 - total MMSE score
- Clinical Dementia Rating (CDR) scale:
 - a 5-point scale used to characterize six domains of cognitive and functional performance applicable to Alzheimer disease and related dementias: Memory, Orientation, Judgment & Problem Solving, Community Affairs, Home & Hobbies, and Personal Care.
 - the following parameters will be summarized/analyzed as outlined in section 6.3:
 - CDR-Sum of Boxes (CDR-SB), derived as the sum of the six individual domain scores and can range from 0 to 18.

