6.2 Parts A and B Combined

The primary endpoint will be summarized by treatment sequence and visit, using the mITT analysis set. All secondary endpoints will be summarized by treatment sequence and visit, using the ITT analysis set. In addition to all summary statistics listed in section 3 above, the 95% confidence intervals for the mean response will be provided.

A plot of the mean concentration of each endpoint over time, along with 95% CI for mean, will be presented by treatment sequence.

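### The Booster group's Part B antibody variable is referenced to before Part A, so it cannot isolate the V13B booster; a paired V12B-to-V15B change is missing

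*Protocol*

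**What the plan says.** Protocol 3.2.2.1 sets the objective: "To assess the immune response triggered by a second ABvac40 booster in patients receiving ABvac40 during Part A". The dosing sections give these patients a single active dose in Part B: "Booster group: One administration at week 16 (V13B"). Their other Part B injections are placebo.

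Protocol 7.1.2.1, like the synopsis, defines the Part B antibody variable as the maximal increment in ELISA signal "with regard to the pre-treatment visit (either V0/V1 [Booster group] or V1B [Delayed start group"). Protocol 7.2.1.1 schedules Part B blood sampling "at visits V1B, V3B, V6B, V9B, V12B, V15B, V16B, V17B, V20B, V21B and V22B (Part B").

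Protocol synopsis and section 4.2.2 note that the V13B booster falls at different times after the last Part A dose. For analysis they group patients as "12 ± 3 months and 18 ± 3 months after their last Part A immunization".

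The SAP sets baseline as the last value before the first dose of study treatment (section 3). It defines the primary outcome for both parts as an increment from baseline (4.2.1). Section 6.1.1, written for Part A, takes the maximum over all visits after baseline. For the combined parts, section 6.2 states: "The primary endpoint will be summarized by treatment sequence and visit, using the mITT analysis set". Secondary endpoints, to which the SAP adds the plasma anti-Aβ40 level, are also summarized by sequence and visit, with 95% CIs for means. Section 2.1.2 mentions the varying booster timing but not the 12- and 18-month groups.

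**The concern.** The objective asks what the second booster triggers. The defined variable asks how far the signal rose above its level before any vaccination. In patients who have already had six active doses these differ: residual Part A antibody enters the increment whether or not the booster does anything. The protocol resets the reference to V1B for the Delayed start group but gives the Booster group no pre-booster reference. Neither document restricts the maximum to visits after V13B.

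At stake is how the exploratory booster result is read. An increment well above zero could be taken as a booster response when it is persistence, and the size of the rise at V13B would have no planned within-patient estimate or interval.

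**Working it through.** **The plan's own figure.** The only size calculation on this antibody measure is for Part A. With SDs of 2.0 and 1.0 the mean variance is (4 + 1)/2 = 2.5. Then n = 2 × 2.5 × (1.960 + 1.036)² / 1.778² = 14.2, so 15 per group, as in Protocol 2.6. It reproduces but does not bear on the Part B reference.

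**Timing.** Five Part B samples (V1B, V3B, V6B, V9B, V12B) precede V13B and six (V15B, V16B, V17B, V20B, V21B, V22B) follow it. V12B is at week 14, V13B at week 16 and V15B at week 18. The last Part A dose is at week 42 (V18). A patient entering Part B at V23 reaches V13B after 77 + 16 − 42 = 51 weeks (11.7 months). One entering at V25 reaches it after 104 + 16 − 42 = 78 weeks (17.9 months). These match the protocol's two groups.

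**What the variable measures.** Let P be the peak Part A increment over V0/V1, R the part still present just before V13B, and b the rise from the booster. The visits over which the Part B maximum runs are not stated.

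- Part B visits only: the increment is at least R even when b = 0.
- Parts A and B: the increment is max(P, R + b), which does not move until b exceeds P − R.

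For scale, assume P = 1.778 OD (the Phase I between-group difference):

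| R/P (assumed) | Part B-only increment with b = 0 | b needed to move the A+B maximum |
|---|---|---|
| 25% | at least 0.44 | 1.33 |
| 50% | at least 0.89 | 0.89 |
| 75% | at least 1.33 | 0.44 |

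**Simulation with a booster effect of exactly zero** (200,000 patients, Part B visits only). Assumptions not in the documents: Part A peak increment gamma-distributed with mean 1.778 and SD 2.0; a stated fraction present at V1B, declining a further 20% over Part B; ELISA SD 0.05 to 0.2 OD. Ranges run over the assay SDs.

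| Fraction at V1B | Mean maximal increment from V0/V1 | Maximum falls before V13B | Mean V15B − V12B | Mean (maximum V15B–V22B) − V12B |
|---|---|---|---|---|
| 0 | 0.08 to 0.32 | 46% | 0.00 | 0.06 to 0.25 |
| 10% | 0.24 to 0.48 | 50 to 60% | 0.00 | 0.05 to 0.24 |
| 25% | 0.50 to 0.73 | 56 to 72% | −0.01 | 0.04 to 0.22 |
| 50% | 0.93 to 1.15 | 63 to 81% | −0.02 | 0.02 to 0.20 |
| 75% | 1.37 to 1.57 | 68 to 85% | −0.03 | 0.01 to 0.17 |

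In the first row nothing persists; the 0.08 to 0.32 OD comes from taking the maximum of eleven noisy readings. The fixed-time paired change sits at zero apart from the small assumed decline. The post-booster maximum minus one reading is biased upward for the same reason as the first row.

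**What the by-visit summaries recover.** In the same patients V0/V1 cancels: mean change at V15B minus mean change at V12B equals the mean of V15B − V12B. The interval is not recoverable. With SD s at each visit and correlation ρ, the paired SD is s√(2(1 − ρ)), and separate visit summaries do not give ρ. Taking s = 2.0, ρ = 0.5 gives a paired SD of 2.0 and ρ = 0.875 gives 1.0. If 35 patients contribute (half of the 70 expected Part A completers), the 95% half-width is 2.032 × 2.0/√35 = 0.69 OD or 2.032 × 1.0/√35 = 0.34 OD. SAP section 3 also summarizes available data only, so the two visit means may come from different patients. Protocol 6.1.1.2 allows a Part B vaccination to be skipped, and SAP 6.2 does not limit the summary to those who received V13B.

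**The case against.** Part B is exploratory, tests no hypothesis and has no success criterion resting on this variable. The SAP takes precedence over the protocol, and its by-visit summaries plus the added plasma level, which needs no V0/V1 reference, would display a group rise across V13B. V0/V1 is a legitimate reference for response over the pre-immune level. The magnitudes rest on assumed persistence, and 1.778 OD comes from Phase I patients who had two or three doses, not six. After 12 to 18 months little antibody may remain.

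All of this stands and limits the point to one missing derived variable. It does not supply the within-patient estimate, its interval or the timing groups. The SAP's separate Day 1 for Part B governs study-day numbering in listings, not baseline.

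Stronger readings are tempting but not supported:

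- *The second-booster objective goes unanswered.* SAP 6.2 allows a descriptive group-level answer.
- *This antibody rise is the only evidence left on memory.* The SAP does record "Levels of antibody secreting cells (only analysed in Part A and not analysed in Part B"), which removes that ex vivo measure from Part B. But plasma anti-KLH and CSF anti-Aβ40 remain in Part B, and Part A has its own booster and cell data.
- *The increment mixes assay runs.* Protocol 7.2.1.1 places titration at V16 and the final Part A visit "and at V22B (Part B), once the samples from all the subjects are available". That says when testing is done. It does not say that V0/V1 samples are left out of the later run, and Protocol 7.2.2 retains samples for repeat analysis.
- *Residual antibody would make patients formal responders in Part B.* Protocol 7.2.1.1 defines Positive Responder status for Part A.

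**Conclusion.** The concern holds in limited form. For the Booster group, the defined variable cannot separate the V13B effect from antibody left by Part A, and the SAP does not supply a booster-specific change. That follows from the definition alone. Its size does not: about 0.5 to 1.6 OD of apparent increment with no booster effect if 25% to 75% of the Part A increment persists, and essentially none attributable to residual antibody if little persists. Persistence, assay SD and the peak distribution are all assumptions. Because Part B is exploratory and group-level summaries are planned, this is a modest improvement and not a defect that invalidates Part B.

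**What to change.** In the SAP, with matching protocol wording, add for Booster-group patients who received V13B the paired change in plasma anti-Aβ40 OD from V12B to V15B. Report the mean with 95% CI, overall and by the protocol's 12- and 18-month groups.

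Beside it, give the matching Part A booster change from V17 (week 40) to V20 (week 44), which also spans two weeks either side of the dose. A maximum-based comparison would be uneven: the Part A booster has three later samples by V23 (V20, V21, V23) against six after V13B.

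Report the maximum over V15B to V22B minus V12B only as supporting description, noting its upward bias. Keep the increment from V0/V1, labelled as response over the pre-immune level.

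The cost is a short text change, one derived variable with its Part A counterpart, and a small table. All samples are already scheduled.
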